#### **7.6.4.2 Neoplasms and Pre-Malignant Lesions**

Malignant neoplasms are summarized by treatment regimen for treated subjects across the on-treatment and long-term follow-up periods combined.

A listing of neoplasms and pre-malignant lesions is also provided for enrolled subjects regardless of diagnosis date. The listing includes exposure to treatment regimens through the event onset. Exposure is measured from the first dose of study therapy to the earlier of the event onset or the end of study therapy.

Neoplasm terms of special interest are identified from 2 sources: (1) all MedDRA preferred terms in the “neoplasms benign, malignant or unspecified” system organ class (SOC) plus the preferred term “hepatic mass”; (2) a list of selected MedDRA preferred terms which represent pre-malignant lesions (see [Table 7.6.4.2-1](#)). The list is generated by searching MedDRA for all terms containing “plasia” or “blood disorder”, and adding these to all terms in the pre-neoplasm

high level term group within the skin and subcutaneous disorders SOC. The resulting list is reviewed and edited by a BMS safety clinician for appropriateness. Note some of these terms also derive from the neoplasms SOC.

All terms are further categorized as benign, malignant, pre-malignant or unclassifiable by a BMS medical monitor, with concurrence from another BMS medical monitor, who are both blinded to treatment regimen.

---

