### 6.2 Treatment Regimens

Treatment regimens are described in Protocol Section 5.1 as ETV treated subjects (ETV) given a starting dose of 0.015 mg/kg up to a maximum dose of 0.5 mg and PBO subjects.

Treatment regimens are defined as follows:

- As-randomized refers to the treatment regimen assigned at randomization. Accrual and efficacy results are presented as-randomized.
- As-treated refers to the actual treatment regimen received. Subjects who receive the incorrect study therapy for the entire period of treatment are grouped according to the treatment regimen associated with the incorrect study therapy. Otherwise, subjects are grouped according to their randomized treatment regimen. Subjects who never receive study therapy have missing as-treated treatment regimen. Results for subject disposition, demographics, baseline characteristics, safety, and PK parameters are presented as-treated. Furthermore, important safety events that occur while a subject is on an incorrect treatment regimen are specifically discussed in the text of the Clinical Study Report.

If a subject receives at least 1 dose of drug in the randomized regimen, then the as-randomized treatment regimen is equal to the as-treated treatment regimen. If  $\geq 5\%$  of treated subjects have as-randomized regimen different than as-treated regimen, summaries are presented by both treatment regimens for select endpoints (see [Section 7](#)).

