- **Year 2 Efficacy Cohort** is treated subjects grouped as-randomized and according to observed Week 48 seroconversion status: ETV, PBO, ETV S48, PBO S48, ETV NS48 and PBO NS48 (S = seroconverter; NS = non-seroconverter). All treated subjects are included in ETV and PBO.
  - **Year 2 Primary Efficacy Cohort** is treated subjects in both Primary and Year 2 Efficacy Cohorts.
- **Year 3 Efficacy Cohort** is observed Week 48 non-seroconverters grouped as-randomized according to observed Week 96 seroconversion status: ETV S96, ETV NS96, PBO S96 and PBO NS96.
- **Year 4 Efficacy Cohort** is PBO-randomized observed non-seroconverters at both Weeks 48 and 96 who seroconverted at Week 144.
- **All ETV Efficacy Cohort** is treated as-randomized ETV subjects and PBO-randomized subjects who received open-label ETV.
- **Post-Year 1 Efficacy Cohort** is treated subjects grouped as-randomized: ETV, PBO, PBO subjects who only received blinded PBO (PBO BL), PBO subjects who received open-label ETV (PBO OL), and All ETV (ETV and PBO OL combined; see previous bullet).
- **Year 2 Safety Cohort** is treated subjects grouped as-treated: ETV, PBO subjects who only received blinded PBO (PBO BL), and PBO subjects who received open-label ETV (PBO OL). In addition, subjects must have received open-label ETV or > 54 weeks of study therapy (the upper bound of the Week 48 visit window; see [Sections 7.4.1](#) and [8.4](#)).
- **All ETV Safety Cohort** is as-treated ETV subjects and as-treated PBO subjects who received open-label ETV.
- **Post-Year 1 Safety Cohort** is treated subjects grouped as-treated: ETV, PBO, PBO subjects who only received blinded PBO (PBO BL), PBO subjects who received open-label ETV (PBO OL), and All ETV (ETV and PBO OL combined; see previous bullet).

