## 7 STATISTICAL ANALYSES

### 7.1 General Methods

All analyses (efficacy, safety and PK) are presented by treatment regimen, ie, ETV vs PBO, based on the appropriate cohort and dataset defined in the earlier section. For Week 48 analysis, all the endpoints are to be cut off through Week 48, unless specified otherwise.

The PK analyses are described in [Section 7.7](#). The methods described below are used to analyze safety and efficacy data.

Categorical variables are summarized either with counts and percents or with proportions (number with event divided by number evaluable) and percents, depending on the endpoint.

Continuous variables are summarized with univariate statistics (eg, n, mean, median, standard deviation, standard error, quartiles, minimum, and maximum).

Longitudinal analyses of efficacy and safety parameters use pre-defined visit week windows (see [Section 8.4](#)). Windows around planned measurement times are constructed based on the

midpoint between planned measurement visits unless specified otherwise. Data are summarized at each scheduled visit through the analysis week.

Analyses of HBV DNA use values only from the central laboratory from the Roche COBAS® TaqMan HBV Test with limit of quantitation (LOQ) of 29 IU/mL and limit of detection (LLD) of 10 IU/mL.

Analyses of laboratory tests and serology use values from the central or local laboratory. Laboratory parameters are summarized using US standard values and units. Refer to [Section 8.11](#) for conversion of select laboratory test values from the Abbott Architect system to the Roche Diagnostics Hitachi Modular system.

Formats of tables, listings and graphs are described in the Data Presentation Plan (DPP).

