### **7.6.4 Other Significant Adverse Events**

#### **7.6.4.1 Events of HBV Disease Progression**

Events of HBV disease progression are summarized by treatment regimen for treated subjects across the on-treatment and long-term follow-up periods combined (see Table 7.6.4.1-1).

---

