### **7.6.7 Growth/Development Assessment**

Growth assessment values and changes from baseline are summarized by treatment regimen at baseline and each scheduled visit (see [Section 8.4](#)) for the following cohorts:

- For treated subjects across the on-treatment and long-term follow-up periods combined
- For the Year 2 Safety Cohort across the on-treatment and long-term follow-up periods combined
- For the All ETV Safety Cohort across the ETV treatment and long-term follow-up periods combined

Growth assessment parameters include HAZ, HAP, WAZ, WAP, BMIAZ, and BMIAP. These parameters are derived using 2000 CDC growth charts.

Longitudinal plots display mean growth changes from baseline in growth assessment (HAZ, HAP, WAZ, WAP, BMIAZ, BMIAP) versus visit week by treatment regimen with error bars representing  $\pm 1$  SE of the reported statistic for treated subjects across the on-treatment and long term follow-up periods combined.

Tanner stage is a development assessment parameter that is summarized analogously by age randomization strata for each staging category (pubic hair, breast/genitals) and treatment regimen (see [Section 7.6.8](#)). Stages I - V are assessed as integers 1 - 5, respectively.

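### The malignancy table, the HBV-progression table and the growth plots keep placebo children in the PBO group after they switch to open-label ETV, which dilutes any ETV vs PBO difference.

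*SAP*

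**What the plan says.** SAP 7.1 sets the default presentation: results are "presented by treatment regimen, ie, ETV vs PBO, based on the appropriate cohort and dataset defined in the earlier section". SAP 6.2 reports safety as-treated, but a child leaves the randomized group only by taking the wrong study therapy for the whole treatment period. "Otherwise, subjects are grouped according to their randomized treatment regimen". A planned switch is not wrong therapy.

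Three outputs apply this label to all treated subjects over the whole study:
- **Malignancy (7.6.4.2):** "Malignant neoplasms are summarized by treatment regimen for treated subjects", with treatment and long-term follow-up pooled.
- **HBV progression (7.6.4.1):** "Events of HBV disease progression are summarized by treatment regimen for treated subjects across the on-treatment and long-term follow-up periods combined". The subgroup summaries in 7.6.8 use the same combined periods.
- **Growth plots (7.6.7):** mean changes by regimen, with error bars of one "SE of the reported statistic for treated subjects across the on-treatment and long term follow-up periods combined".

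The on-treatment period (6.1) runs to the last dose of study therapy plus 5 days. Study therapy includes open-label ETV (8.9). Long-term follow-up then runs to the end of the study.

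The groups that would separate exposure already exist. The definition of the Post-Year 1 Safety Cohort in 6.3 reads: "is treated subjects grouped as-treated: ETV, PBO, PBO subjects who only received blinded PBO (PBO BL), PBO subjects who received open-label ETV (PBO OL"), with All ETV as a further group. The All ETV Safety Cohort and the Year 2 Safety Cohort (ETV, PBO BL, PBO OL) are defined there too.

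**The concern.** Protocol 4.1 moves every child without HBeAg seroconversion to open-label ETV at the Week 52 assessment. Most of the placebo arm is therefore on ETV from the second year, and any later event in those children is tabulated under PBO.

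The outcomes affected are the ones for which late events matter most. Protocol 1.5 says the ETV risk assessment rests mainly on the pre-clinical findings, describes tumours in rodents, and calls the long-term malignancy risk unknown. Long-term safety is a secondary objective. For the adult rollover studies, the same section rules out comparing malignancy by arm because treatment histories were mixed. The 7.6.4.2 table invites that kind of comparison here.

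**Working it through.** **1. The plan's own cascade (SAP 5).** Inputs: 10% dropout per year and 10% placebo seroconversion.
- Reach Week 48: 20 × 0.9 = 18.
- Switch to open-label ETV: 18 × 0.9 = 16.2, stated as 16.
- Complete 48 weeks of open-label ETV: 16 × 0.9 = 14.4, stated as 14.

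The stated 18, 16 and 14 reproduce.

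**2. Switchers in the full trial.** With 60 placebo children (Protocol synopsis), 60 × 0.9 × 0.9 = 48.6, or 81%. The range is 72% (10% dropout, 20% seroconversion) to 99% (no dropout, 1% seroconversion).

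**3. Person-time in the PBO column.** Assumptions: dropout stays at 10% per year as a constant hazard λ = −ln(0.9) = 0.1054 per 52-week year, the switch is at Week 52, and the study lasts 264 weeks (5.077 years).
- Weeks 0-52: 60 × (1 − 0.9)/λ = 56.9 person-years.
- Weeks 52-264: 60 × (0.9 − 0.9^5.077)/λ = 60 × (0.9 − 0.586)/0.1054, about 179 person-years.
- Non-switchers hold 10% of the latter (17.9) and switchers 90% (161.1).
- Column total: 56.9 + 17.9 + 161.1 = 235.9.
- Share after first ETV dose: 161.1/235.9 = 68%.
- Share before or without ETV: 56.9 + 17.9, about 75 person-years.

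Range for that share: 61% (10% dropout, 20% seroconversion) to 80% (no dropout, 1% seroconversion).

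**4. Dilution (illustrative, since the documents give no event rates).** Suppose ETV multiplies an event rate by R from the first dose onward. With f = 0.683, the ratio between the columns is R/(1 − f + fR).
- R = 2: 2/1.683 = 1.19.
- R = 3: 3/2.366 = 1.27.
- R = 5: 5/3.732 = 1.34.
- R = 0.5 (a benefit): 0.5/0.6585 = 0.76.

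**5. Size of an ETV-exposed group.** 120 + 48.6, about 169 children. With the same dropout in the ETV arm, person-time is 2 × 235.9 + 161.1, about 633 person-years.

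**The case against.** The case on the other side is substantial.

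- **Events are tabulated by ETV exposure elsewhere.** Protocol 7.1.1 sends cancers to the SAE form, and 7.3.1 continues SAE reporting in long-term follow-up. SAP 7.6.2 summarizes SAEs for the Year 2 and All ETV Safety Cohorts on treatment, and for the Post-Year 1 Safety Cohort in follow-up. HBV-progression events are defined by AE preferred terms, so they enter the parallel tables in 7.6.5. The neoplasm listing gives exposure up to onset. This stands: the weakness is in comparative presentation, not capture. What remains is that treatment and follow-up sit in separate tables, and exposure-adjusted rates (7.6.2, 7.6.5, 8.10) cover on-treatment events only.
- **Growth tables are already split.** The line "For treated subjects across the on-treatment and long-term follow-up periods combined" is the first of three cohorts in 7.6.7. The other two are the Year 2 and All ETV Safety Cohorts, also with follow-up. This stands, so only the plots are affected.
- **The outputs are descriptive and keep the randomized groups.** No test is planned on them, and the tables on blinded therapy through Week 48 stop at the first open-label dose. A randomized-group table is a legitimate complement. That argues for keeping it, not for having it alone.

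A reader might infer that harms on ETV are charged to placebo throughout the safety report. The documents do not support that, for the reasons above. A reader might also infer that 80% of PBO time is time on ETV, from (264 − 52)/264. That fraction applies only to a switcher who completes 264 weeks, and it measures time since first ETV dose. A switcher who does not seroconvert takes at most 96 weeks of ETV (36% of 264). The longest course, Week 52 to Week 192, is 140 weeks (53%).

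**Conclusion.** The point holds for the malignancy table, the HBV-progression table and the growth plots, and no further. In these outputs about four in five placebo children would contribute ETV-exposed time under a PBO label, about 68% of that column's person-time (range 61-80%). The effect is mainly dilution. A true doubling of a rate would appear as about 1.2, and for HBV progression a benefit of ETV would be blurred as readily as a harm.

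The 81% rests on the plan's own rates. The 68% also assumes that 10% yearly dropout persists for five years. The rate ratios also assume an effect that starts at the first dose and lasts. Efficacy conclusions and the Week 48 safety comparison are untouched. The change should be made, because no specified malignancy or HBV-progression summary joins ETV treatment and follow-up over an ETV-exposed denominator.

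**What to change.** - **SAP 7.6.4.1 and 7.6.4.2:** keep the existing ETV and PBO columns, labelled as randomized groups. Add PBO before any ETV, PBO OL from the first open-label ETV dose, and All ETV from the first active ETV dose through long-term follow-up. Give person-years and events per 100 person-years for each. The rate in 8.10 uses time on study therapy only, so state that follow-up time is included here.
- **SAP 7.6.7, plots only:** show PBO BL and PBO OL as separate lines from the switch. Add a note that PBO BL after Week 52 consists mainly of children selected on Week 48 seroconversion and is not a randomized comparator.
- **Rescue and other alternative ETV:** the dose dates in 8.9 exclude rescue ETV, so state how time after it is classified. The start date of alternative ETV therapy is already derived there.

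The cost is SAP wording and reprogramming of two tables and one set of plots. The dates and cohorts exist, and no data collection or conduct changes. The downside is a few more columns with sparse events, and a PBO-before-ETV denominator of only about 75 person-years, too small to serve as a firm comparator for rare events.

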The primary and key secondary analyses will be based on treated subjects (modified intention-to-treat [ITT]). For the analysis of the primary and key secondary endpoints at Week 48, subjects who discontinue from study prior to Week 48 or have missing Week 48 measurements will be considered failures at Week 48 (Non-completer = Failure). Sensitivity analyses will be performed in order to account for possible effects of early discontinuation, in which subjects who discontinue from study prior to Week 48 or have missing Week 48 measurements are excluded (Non completer = Missing). Treatment comparisons for the primary endpoint and key secondary endpoints will be stratified by age group using Cochran-Mantel-Haenszel (CMH) weights and $NC=F$. The difference in proportions (ETV - placebo), p-value, and 95% Confidence Interval (CI) will be presented. ETV will be considered superior to placebo if the p-value is < 0.05 . The CI for the differences in proportions will be based on the normal approximation to the binomial distribution. On-treatment efficacy endpoints are assessed based on double-blind or open-label ETV therapy, and therefore exclude rescue open-label ETV during long-term follow-up.

Serious adverse events and deaths will be reported for enrolled subjects. Other safety analyses will be based on treated subjects. Discontinuations due to adverse events will be summarized. Adverse events will be reported by severity and relationship to study medication. Laboratory abnormalities will be summarized.

Pharmacokinetic samples will be collected at specified times to further evaluate and characterize the pharmacokinetics of ETV in pediatric subjects. The PK data collected in the study will be combined with the PK data collected in the pediatric study AI463028 to help develop a population pharmacokinetic/pharmacodynamic model in pediatric nucleos[t]ide naive subjects.

[figure not shown]
[figure not shown]
There will be an external data monitoring committee (DMC) for this study.

TABLE OF CONTENTS

TITLE PAGE	1
DOCUMENT HISTORY	2
SYNOPSIS.....	4
TABLE OF CONTENTS	7
1 [REDACTED]	[REDACTED]
1.5 Overall Risk/Benefit Assessment	19
2 STUDY OBJECTIVES.....	22
2.1 Primary Objective	22
2.2 Secondary Objectives.....	23
3 ETHICAL CONSIDERATIONS	23
3.1 Good Clinical Practice	23
3.2 Institutional Review Board/Independent Ethics Committee	24
3.3 Informed Consent	24
4 INVESTIGATIONAL PLAN.....	25
4.1 Study Design and Duration.....	25
4.1.1 Subject Management Decisions.....	28

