Given its favorable clinical safety profile, the risk assessment for ETV is primarily concerned with specific findings from the pre-clinical evaluation. In rodent carcinogenicity studies using lifetime dosing, ETV was associated with statistically increased rates of tumors for both mice and rats with 2 distinct patterns observed. First, a specific pattern of lung tumor development was observed only in mice and at low exposure multiples (ranging between 4 and 5 times the exposure in humans at 0.5 mg daily, or between 2 and 3 times the exposure in humans at the 1.0 mg dose, depending on whether the multiples are calculated in relation to patients or healthy subjects respectively). Second, multiple tumor types occurred in both mice and rats, but only after lifetime exposure at high exposure multiples.^{37,38} The results of investigative studies suggest that lung tumors observed in mice at low exposure multiples result from unique effects of ETV on the mouse lung; whereas tumors in rodents occurring only at high doses/exposures may result from biochemical actions that are likely to demonstrate a biological threshold (eg, are not expected to occur below a threshold dose). Observed malignancy rates for ETV- and LVD-treated patients from the ETV development program (1755 ETV patients observed for a mean of 77.6 weeks, including a mean treatment duration of 60.4 weeks; 1160 LVD patients observed for a mean of 71.6 weeks,

including a mean treatment duration of 59.5 weeks) are comparable across the 2 treatment groups and these rates fall within the expected range for malignancies based on epidemiologic studies in populations with chronic HBV infection.³⁹

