4.1.2 Subjects Experiencing Significant Elevations Of ALT Due To Acute Exacerbation of CHB

A subject who experiences an extreme elevation of ALT due to acute exacerbation of CHB should be carefully managed at the discretion of the primary investigator. Additional laboratory testing and frequent clinical evaluations are recommended (See [Figure 5.3.2.1](#)).

- An extreme elevation of ALT due to acute exacerbation of CHB is defined as:
 - a serum ALT > 1,000 U/L,OR
 - an elevation in serum ALT > 20x ULN WITH associated clinical or laboratory findings suggestive of hepatic dysfunction,
- Upon investigator request and after discussion and approval by the BMS Central Medical Monitor:
 - A subject who experiences an extreme elevation of ALT due to acute exacerbation of CHB will be provided access to rescue open-label ETV.

The choice of anti-HBV therapy to be used to treat an extreme elevation of ALT due to acute exacerbation of CHB remains at the discretion of the investigator. Only open-label ETV will be provided by the sponsor, and will be limited to those subjects who do not have access to acceptable alternative anti-HBV therapy. Subjects started on rescue open-label ETV will be provided the drug for up to 96 consecutive weeks. Upon completion of the rescue open-label ETV course, subjects will remain on study as part of the LTFU phase until they complete a total of 5 years of study participation from the start of blinded treatment or 48 weeks beyond the completion of rescue open-label ETV; whichever is later. During this time, subjects may be treated with alternative anti-HBV therapy at the discretion of their primary investigator. The sponsor reserves the right to terminate access to rescue open-label ETV if any of the following occur: a) the study is terminated due to safety concerns; b) the subject can obtain medication from a

government sponsored or private health program; or c) therapeutic alternatives become available in the local market.

Specific decisions regarding the management of an extreme elevation of ALT due to acute exacerbation of CHB remain at the discretion of the subject's primary investigator but access to rescue open-label ETV must be discussed with and approved by the BMS Central Medical Monitor.

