## 6 STUDY PERIODS, TREATMENT REGIMENS AND POPULATIONS FOR ANALYSES

### 6.1 Study Periods

Study periods for efficacy and safety analyses are defined as follows:

- **Pre-treatment period** begins at the first visit until initiation of study therapy.
- **On-treatment period** begins after the first day of study therapy and ends at the last dose of study therapy plus 5 days.
- **ETV treatment period** begins after the first day of active ETV and ends at the last dose of active ETV plus 5 days.
- **Off-treatment follow-up period** begins on the last dose of study therapy plus 6 days and ends at the start of alternative anti-HBV therapy minus 1 day.
- **Long-term follow-up period** begins on the last dose of study therapy plus 6 days until the end of the study.
- **Alternative ETV follow-up period** begins on the later of the last dose of study therapy plus 6 days and the start of alternative ETV therapy, until the end of the study.

Note that rescue open-label ETV is considered alternative anti-HBV therapy. See [Section 8.9](#) for additional conventions.

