### 7.4.1 Study Therapy

Extent of exposure to study therapy is summarized for blinded therapy (ETV active or PBO), open-label ETV, active ETV (blinded active ETV or open-label ETV), and all therapy (blinded therapy or open-label ETV) by treatment regimen as follows:

- Time on therapy (weeks):  $(\text{last dose date of drug} - \text{first dose date of drug} + 1)/7$ .
- Cumulative dose: total amount (mg) of drug summed across dosing records.
- Average daily dose: cumulative dose divided by time on therapy.

Extent of exposure to study therapy is also summarized analogously for the following: Primary Cohort; All ETV Safety Cohort; by age randomization strata for each treatment regimen.

Time on study therapy is also described by a Kaplan-Meier plot and life table. Discontinuations from study therapy are considered events in this analysis, and are identified by subjects with non-missing last dose date of study therapy. For subjects who have not discontinued, time on study therapy is censored at the maximum of the last dose date of study drug (ETV blinded active or PBO, ETV open-label).

Time in long-term follow up is summarized by treatment regimen for long-term follow-up subjects in the Post-Year 1 Safety Cohort. Time in long-term follow-up (weeks) is defined as (last contact date - last dose date of study therapy)/7.

Time in off-treatment follow up is summarized by treatment regimen for off-treatment follow-up subjects in the Post-Year 1 Safety Cohort. Time in off-treatment follow-up (weeks) is defined as (minimum(last contact date, start date of alternative anti-HBV therapy - 1) - last dose date of study therapy)/7.

Dose interruptions of study therapy more than 3 days are summarized by treatment regimen. Reasons for interruption are also identified.

See [Section 8.9](#) for additional conventions.

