## 8.9 Derived Dates

Derived dates that are used commonly in analyses are defined as follows. Derivations of dose dates exclude rescue open-label ETV.

- First dose date of study therapy is the earliest start date of drug (ie, blinded therapy [ETV active or PBO] or open-label ETV) identified from valid dosing records, ie, non-missing start date and number of units per day > 0, from blinded therapy study medication CRFs. This date is used to identify treated subjects and to distinguish measurements across study periods. Note that this is also first dose date of blinded study therapy.

- Dose end date of study therapy is the latest start or end dates of drug (ie, blinded therapy [ETV active or PBO] or open-label ETV) identified from valid dosing records, ie, non-missing start or end date and number of units per day > 0 or total dose > 0. This date is used to assess time on study therapy.
- Last dose date of study therapy is the dose end date of study therapy derived only for subjects with an end of treatment subject status CRF indicating whether the subject completed the treatment period. This date is used to exclude data in antiviral activity and safety analyses, and to distinguish measurements across study periods.
- Dose end date of blinded therapy is the latest start or end date of blinded therapy (ETV active or PBO) identified from valid dosing records, ie, non-missing start or end date and number of units per day > 0, from blinded therapy study medication CRFs. This date is used to assess time on blinded study therapy.
- First dose date of open-label ETV is the earliest start date of open-label ETV identified from valid dosing records, ie, non-missing start date and total dose > 0, from open-label study medication CRFs. This date is used to distinguish measurements across blinded vs open-label treatment, and to assess time on open-label therapy.
- Dose end date of open-label ETV is the latest start or end date of open-label ETV identified from valid dosing records, ie, non-missing start or end date and total dose > 0, from open-label study medication CRFs. This date is used to assess time on open-label therapy.
- First dose date of active ETV is the first dose date of study therapy for ETV-randomized subjects, and the first dose date of open-label ETV for PBO-randomized subjects. This date is used to identify all ETV-treated subjects and to distinguish measurements across study periods.

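### The neoplasm listing stops counting exposure at the end of study therapy, so a tumour arising during or after rescue is listed without up to 96 weeks of ETV, or with no ETV at all for a placebo child rescued before open-label treatment

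*SAP*

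**What the plan says.** SAP 7.6.4.2 has two displays. Malignant neoplasms are summarised by treatment regimen over the on-treatment and long-term follow-up periods together. There is also a subject listing: "A listing of neoplasms and pre-malignant lesions is also provided for enrolled subjects regardless of diagnosis date." The listing is meant to show exposure up to onset, and the rule for it is: "Exposure is measured from the first dose of study therapy to the earlier of the event onset or the end of study therapy."

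Two other sections settle what study therapy means. SAP 6.1: "Note that rescue open-label ETV is considered alternative anti-HBV therapy." SAP 8.9: "Derivations of dose dates exclude rescue open-label ETV." SAP 8.9 also takes blinded, open-label and rescue dosing from separate case report forms. For a placebo-randomised child, active ETV starts with the first open-label dose.

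On duration, Protocol 4.1.2 states: "Subjects started on rescue open-label ETV will be provided the drug for up to 96 consecutive weeks." Protocol 5.3 doses rescue by the same table as study ETV. The notes to Protocol Figure 5.3.2.1 move a rescued child into long-term follow-up at once, so study therapy has ended by then.

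SAP 7.4.1 summarises exposure to blinded, open-label, active and all study therapy. The SAP has no summary of time on rescue or other alternative ETV.

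**The concern.** The listing keeps collecting tumours throughout follow-up, while its exposure clock stops when study therapy stops. For a rescued child, the drug under assessment continues for up to 96 weeks after the clock has stopped.

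This bears on the risk the protocol ranks first. Protocol 1.5 says "the risk assessment for ETV is primarily concerned with specific findings from the pre-clinical evaluation", describes tumours in mice and rats, and calls the long-term human malignancy risk unknown. Few tumours would be expected in a trial of about 180 children, so each would be judged line by line. Exposure before onset is the figure a reader would look at.

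The sharpest case is a placebo child rescued before any open-label ETV. The listing would show placebo time only, although the child may have taken ETV for most of two years, and the by-regimen summary would place a malignancy under placebo. The SAP expects such children: SAP 7.5.1 has an efficacy sensitivity analysis for placebo subjects who start rescue by Week 48. It makes no matching provision for exposure in the neoplasm listing.

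**Working it through.** **1. The plan's own figure.** Protocol 4.1 and 4.1.1 allow 96 weeks of study ETV plus 48 weeks of consolidation: 96 + 48 = 144 weeks. This matches the 144-week maximum in the Protocol Synopsis, which does not count rescue.

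**2. What the listing counts.**

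| Source of ETV | Counted? | Basis |
|---|---|---|
| Blinded active ETV | yes | SAP 8.9, study therapy |
| Open-label ETV | yes | SAP 8.9, study therapy |
| Rescue open-label ETV | no | SAP 6.1 and 8.9 |
| Other ETV in follow-up | no | SAP 8.9, alternative therapy |

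**3. Size per child.** Let S be weeks of study ETV and R weeks of rescue before onset. The listing reflects S, the child has received S + R, and the share missing is R/(S + R). With a full course, R = 96:

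| Child | S | S + R | Missing |
|---|---|---|---|
| ETV arm, with consolidation | 144 | 240 | 96/240 = 40% |
| ETV arm, 96-week course | 96 | 192 | 96/192 = 50% |
| ETV arm, rescued at Week 24 (assumed time) | 24 | 120 | 96/120 = 80% |
| Placebo, open-label from about Week 52 to Week 192 | 140 | 236 | 96/236 = 41% |
| Placebo, rescued before any open-label ETV | 0 | 96 | 96/96 = 100% |

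For the open-label placebo row I assume the listing separates placebo from ETV time. The rule itself runs from the first dose of study therapy, which for that child is placebo.

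Shorter courses omit less. After a 96-week study course, 24 weeks of rescue before onset gives 24/(96 + 24) = 20%, and 48 weeks gives 48/(96 + 48) = 33%. With S = 0 the share is 100% for any R.

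**4. Whether such events can be observed.** The longest ETV-arm total, 240 weeks, fits within the 264-week study. Protocol 4.1.2 keeps rescued children on study for at least 48 weeks after rescue ends, so tumours arising after a full course can enter the listing.

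**5. How the placebo child is classified.** With no open-label dose, no first date of active ETV is derived (SAP 8.9). The child is outside the All ETV Safety Cohort and belongs to the blinded-placebo-only group (SAP 6.3). Safety is presented as treated, which here means placebo (SAP 6.2). A malignancy therefore counts under placebo in 7.6.4.2. The same grouping holds for placebo children switched to open-label ETV, but they have derived ETV dates and belong to the All ETV cohort. The rescue-only child has neither.

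**The case against.** The SAP does handle safety after rescue. Sections 6.1 and 6.3 define an alternative ETV follow-up period and cohort covering rescue and concomitant ETV. SAEs (7.6.2), adverse events (7.6.5) and laboratory abnormalities (7.6.6.1) are tabulated for it, and Protocol 7.1.1 has cancers reported on an SAE form. SAP 7.4.2 also summarises alternative anti-HBV medications in follow-up. A reader might infer that tumours after rescue drop out of the safety report, and these sections show otherwise. They give no duration of ETV, however, and do not tie exposure to tumour onset. In their groupings the rescue-only placebo child remains outside All ETV.

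A reader might also infer that the 7.4.1 exposure tables are wrong. They are labelled as study therapy, and time on study therapy is the denominator for the exposure-adjusted rates in 8.10, which count on-treatment events. Adding rescue time there would dilute those rates. This part of the objection stands in full.

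Nor do the documents support saying that the SAP contradicts the protocol. The Protocol Synopsis says "On-treatment efficacy endpoints are assessed based on double-blind or open-label ETV therapy, and therefore exclude rescue open-label ETV" during long-term follow-up. That is a rule for efficacy and sets none for safety exposure. Protocol 8.4.2 itself ends off-treatment follow-up when alternative therapy starts. Keeping rescue outside study therapy is coherent, but nothing in the protocol requires the neoplasm listing to ignore it.

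Could open-label ETV in the SAP be read to include rescue? The separate forms and definitions in 8.9 rule that out. Listing formats are in a Data Presentation Plan that is not among the documents, so rescue dates might be displayed there. The exposure rule in the SAP would still omit rescue.

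**Conclusion.** The point holds for the neoplasm displays. Applied as written, the rule omits up to 96 weeks of rescue ETV, plus any other ETV taken later, from the exposure shown for a tumour arising during or after rescue. With a full course before onset, 40% to 50% of ETV received is missing after a complete ETV-arm study course. All of it is missing for a placebo child rescued before open-label ETV, whose malignancy is also summarised under placebo.

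These are per-child maxima. Rescue requires an extreme ALT elevation, no acceptable alternative therapy and the medical monitor's approval, and the sponsor can end access early. The documents give no count of rescued children, so the effect across the trial is unknown and the percentages do not estimate a trial-level bias. It would also be wrong to conclude that the affected children are generally those with the longest ETV exposure: a rescue-only child has at most 96 sponsor-supplied weeks, against 144 for an ordinary consolidation course. No test, event count or on-treatment rate changes. What changes is how a tumour would be read against the protocol's main stated risk, and for that reason the change is worth making.

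**What to change.** In the SAP 7.6.4.2 listing, add cumulative ETV exposure to event onset from all sources: blinded active, open-label, rescue and, where dates allow, concomitant ETV. Show it separately from placebo time, with time since the last ETV dose.

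In both the listing and the malignant-neoplasm summary, flag or footnote placebo-randomised subjects who received rescue or other alternative ETV before onset.

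Add a separate descriptive summary of time on rescue or alternative ETV for the alternative ETV follow-up cohort.

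Leave the study-therapy exposure in 7.4.1, the rate denominators in 8.10 and the study-period dates in 8.9 as they are.

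The cost is SAP wording and modest programming. Rescue dosing forms exist (SAP 8.9), and anti-HBV medications are already collected in follow-up (Protocol 6.3.3). SAP 8.9 derives only start dates for rescue and alternative ETV, so stop dates must be added. Some for concomitant ETV will need imputation, under date conventions that SAP 8.1 leaves to be supplied. Efficacy analyses are unaffected.
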